A randomization schedule stratified by presence vs. absence of ADHD, presence vs. absence of concomitant stimulant treatment (within the ADHD group), and pre-pubescent vs. post pubescent (as determined by the Tanner Questionnaire with scores of 1-2 representing pre-pubescent and scores of 3-5 indicating post-pubescent) will be developed by the on-site biostatistician and will be used to assign omega-3 fatty acids (N=30) or placebo (N=30) treatment in a double-blind manner. We will stratify treatment assignment by some of the independently transmitted variables that contribute to the heterogeneity of at-risk adolescents (i.e. ADHD and concomitant use of stimulants) so that we will be able to assess the effects of these clinical factors on the neurophysiological and omega-3 fatty acid RBC level changes associated with supplementation of omega-3 fatty acids (vs. placebo) and examine potential neurophysiological markers of treatment response within clinically defined subgroups. We selected these variables for stratification because they may each affect outcome and treatment response.

Twelve-week Study Phase: During the 12-week DBPC phase subjects will participate in weekly research visits to assess symptom response and adverse side effects. Following the randomization visit, all visits will be scheduled weekly (or ≤ 10 days apart). The research visits will take approximately 1 hour; at these visits an experienced clinician will evaluate the patients for adverse effects and clinical response. Efficacy assessments will be obtained by a rater who is blind to side effects.

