Two-week and Long-term Follow-up: At the end of the 12 weeks patients and their legal guardians (if < 18 years) will decide whether they would like to continue (or start for those receiving placebo) omega-3 fatty acids. Regardless of the treatment chosen, all patients will return for a follow-up visit two weeks following their last visit in the DBPC study to ensure that there has been no significant worsening of their mood. Importantly, all patients will have the option to continue to participate in the BITREC, which is a longitudinal 5-year study. Since some patients will opt to continue omega-3 fatty acid treatment, this will permit us to obtain long-term effectiveness and tolerability data. Safety and efficacy assessments will be performed at all follow-up visits. Subjects will be responsible for obtaining their own omega-3 fatty acids supplementation after study completion if they wish to continue with omega-3 treatment. Omega-3 fatty acids are widely available via food, health, and supplement retail stores at a relatively low cost.

Assessments:

The Children's Depression Rating Scale-Revised (CDRS-R), a 17-item observer-rated questionnaire,^{40,41} and the

Young Mania Rating Scale (YMRS),⁴²⁻⁴⁴ an 11-item observer-rated questionnaire to assess depressive and manic symptoms, respectively. A consensus adolescent/legal guardian score for the CDRS-R and YMRS will be determined by the rater.

Subjects will also be rated using the Clinical Global Impression-Severity Scale (CGI-S), a clinician rated 7-point scale (rated from 1=normal to 7=extremely ill) to assesses overall illness severity.⁴⁵ CDRS-R, YMRS, and CGI-S will be administered at screening, baseline (concurrent with the first imaging session) and then subsequently at each weekly follow-up visit and will be used to rate symptoms during the prior week.

The CGI-Improvement Scale (CGI-I) is a clinician rated scale that assesses overall illness change

from baseline and will be administered at all post-baseline visits.

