Spectral Analysis: We have implemented a spectral fitting routine that uses an iterative, non-linear, Marquardt-Levenberg algorithm in combination with prior spectral knowledge to precisely fit acquired spectra. The spectral model allows for the inclusion of various constraints in the spectral model such as spectral linewidths, phase/frequency offsets and lineshapes. The model template will be iteratively fitted to the raw data until the minimum residual (within an acceptable level of tolerance) between the raw and modeled data is reached. The fitting algorithm accounts for both zeroth- and first-order phase, thus alleviating the need for prior filtering, Fourier-Transformation and phase-correction of the data. If the spectrum from an entire anatomical structure is to be studied, multiple spectra can be collected and summed from the structure of interest. For maximal signal coherence, each spectra will first be corrected for zeroth-order phase shifts resulting from point-spread effects, as well as for frequency shifts resulting from B₀ inhomogeneity, prior to summing.

b. Data Analyses and Data Monitoring:

Data Analyses

Prediction 1: Omega-3 fatty acid supplementation will be more effective than placebo for the treatment of mood symptoms in adolescents with a high risk for developing mania. A mixed effects model repeated measures (MMRM) approach will be used to compare change over time in CDRS-R (and YMRS) scores between treatment (omega-3 vs. placebo) groups. Covariates for these models will be time of assessment (study week) and treatment group. A mixed model approach will account for missing information while adjusting for the correlation of observations over time. We will also use MMRM to compare change over time in total mood burden rating. We will evaluate other potential covariates and confounds as described and will specifically examine the effects of co-occurring ADHD and anxiety disorders, and concomitant use of stimulants within groups. We will also compare treatment group differences in change from baseline to endpoint in YMRS and CDRS-R scores using an analysis of variance (ANOVA). This analysis will provide information without the necessary assumptions of the MMRM model regarding missing data and fitting the regression. We will calculate the effect sizes of group differences for change in CDRS-R and YMRS using the formula $d = (\text{mean change from baseline to endpoint group 1} - \text{mean change from baseline to endpoint$

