Exploratory analyses: In order to examine the potential impact of missing data on analyses, we will determine whether there are significant differences in demographic or clinical variables between completers and non-completers within and between treatment groups. We will examine the effect of any variables that differ and adjust analyses as necessary. Additionally, we will perform sensitivity analyses to determine whether missing data in the form of unknown changes in neurophysiologic parameters influenced our findings. Specifically, in regression analyses where change in mood symptom rating is predicted from change in a neurophysiologic and biological measure four analyses will be performed: No imputation (only available data is used), group mean imputation (for each missing change value, the mean change value of the corresponding treatment group will be substituted), and zero substitution (a change of zero is assumed for each missing change value). Additionally, associations between baseline neurophysiologic measures and subsequent “missingness” will be evaluated using regression analyses, predicting “missingness” on later scans from the baseline value, change in symptom ratings, and treatment assignment). We will also compare baseline neurometabolite levels (NAA, mI, Glu, Cho, and Cr) within each VOI in the subjects with a demographically matched subgroup of healthy control adolescents from the BITREC in order to determine the direction of any changes that occur in the subjects (i.e. whether they normalize following treatment with omega-3 fatty acids) using a separate regression for each VOI, with neurometabolite levels as the dependent variables and group (baseline at-risk adolescents with MDD vs. healthy controls) as the independent variable. Additionally, we will use multiple regression models to analyze associations between baseline neurochemical levels and omega-3 blood levels with change in mood and behavior rating in each treatment group. The treatment by change in rating scale interaction term will be the primary measure of interest. We will also explore the effects of nicotine use, illness duration, and change in behavioral, functional, and pilot mood burden measures on changes in omega-3 fatty acid levels and neurometabolite levels. Because these exploratory analyses are hypothesis-generating secondary analyses, we will use a standard 0.05 significance level as a threshold for interpreting interactions that may warrant further study. For all analyses, we will visually inspect plots of data points to identify outliers and will examine their clinical and neurophysiologic characteristics to determine their relevance to understanding treatment effects. We will examine the impact of clinical factors (e.g. ADHD and other co-occurring diagnoses) that may contribute to neurophysiologic, RBC fatty acid levels or efficacy findings as effect moderators. We will also conduct analyses of treatment group as a possible *moderator* of the association between changes in metabolite levels and mood symptoms. Moderator models allow the strength (possibly

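### The Prediction 1 mood models commit to neither baseline score nor the randomisation strata as covariates: a cheap gain in precision left open, not a bias

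*Combined protocol and SAP*

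**What the plan says.** Section E.b, Prediction 1, compares CDRS-R and YMRS over time between arms with a repeated-measures mixed model (MMRM). Its committed terms are: "Covariates for these models will be time of assessment (study week) and treatment group". Beyond that the text is open: "We will evaluate other potential covariates and confounds as described". ADHD, anxiety disorders and stimulant use are to have their effects examined, without being fixed as model terms. The supporting analysis has no covariates: "We will also compare treatment group differences in change from baseline to endpoint in YMRS and CDRS-R scores using an analysis of variance (ANOVA". The plan presents it as a check that avoids the mixed model's assumptions, and it defines the effect size d on raw mean change.

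The covariates in question already exist. Under Assessments, "CDRS-R, YMRS, and CGI-S will be administered at screening, baseline (concurrent with the first imaging session", and the schedule in Figure 1 agrees. Section E.a, Screening, Baseline, & Randomization, describes "A randomization schedule stratified by presence vs. absence of ADHD, presence vs. absence of concomitant stimulant treatment" (the latter within the ADHD group), together with "pre-pubescent vs. post pubescent (as determined by the Tanner Questionnaire". The reason given is: "We selected these variables for stratification because they may each affect outcome and treatment response".

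Under Exploratory analyses, "We will examine the impact of clinical factors (e.g. ADHD and other co-occurring diagnoses" covers ADHD as a possible moderator. Pubertal status is not mentioned in any supplied analysis text.

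**The concern.** The plan stratifies on factors it believes may be prognostic and measures both scales at baseline in everyone, yet no Prediction 1 model is bound to use this information. Evaluating or examining a covariate is not a commitment to adjust for it, so the choice can be made after the data are seen. In a trial of 60, two things could be lost. A change-score comparison is less precise than baseline adjustment unless the regression slope of endpoint on baseline is 1. Prognostic strata left out of the model stay in the residual variance.

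**Working it through.** **Plan's own figure.** There is none to reproduce. Section F.2 gives 30 per arm, but the supplied text states no power, alpha, sidedness or SD for Prediction 1.

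**Inputs from the documents.**
- N = 60 randomised (F.2).
- 25% loss, so 0.75 × 60 = 45. This is a lower bound for mood endpoints, because the 25% also counts unusable spectroscopy.
- d = 0.6, the low end of the range called clinically relevant (F.2).
- Strata: 3 levels (ADHD/stimulant) and 2 levels (puberty). Main effects use 2 + 1 = 3 df, and baseline uses 1, making 4.

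**Assumed, because not given.**
- Baseline-endpoint correlation ρ of 0.3, 0.5 or 0.7.
- k = baseline SD / endpoint SD of 1, 0.7 or 0.5. Values below 1 allow for the CDRS-R ≥ 28 entry rule narrowing the baseline. Excluding past mania or hypomania may do the same for YMRS.
- Two-sided alpha of 0.05.

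**Step 1: change-score analysis, before any df cost.**
Var(ANCOVA) / Var(change) = (1 − ρ²) / (1 + k² − 2ρk)

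| k | ρ = 0.3 | ρ = 0.5 | ρ = 0.7 |
|---|---|---|---|
| 1 | 0.91/1.40 = 0.65 | 0.75/1.00 = 0.75 | 0.51/0.60 = 0.85 |
| 0.7 | 0.91/1.07 = 0.85 | 0.75/0.79 = 0.95 | 0.51/0.51 = 1.00 |
| 0.5 | 0.91/0.95 = 0.96 | 0.75/0.75 = 1.00 | 0.51/0.55 = 0.93 |

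The denominator minus the numerator is (k − ρ)², so the ratio never exceeds 1. It equals 1 when ρ = k.

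**Step 2: after the df cost.** Simulation, 6,000 trials per case. Assumptions: strata shares 0.50/0.25/0.25 and 0.25/0.75, no stratum effect on outcome, allocation alternating within stratum, ANCOVA on baseline plus 3 stratum terms.

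| Case | ρ = 0.3 | ρ = 0.5 | ρ = 0.7 |
|---|---|---|---|
| N = 60, k = 1 | 0.661 | 0.772 | 0.870 |
| N = 60, k = 0.7 | 0.865 | 0.965 | 1.023 |
| N = 45, k = 1 | 0.670 | 0.772 | 0.877 |
| N = 45, k = 0.7 | 0.883 | 0.988 | 1.035 |

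The worst cases are about +2% at N = 60 and +4% at N = 45. The k = 0.5 case is covered by formula only. Its worst ratio is the same 1.00, so a similar cost is expected.

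**Step 3: power at d = 0.6 on the SD of change.** Noncentral t with ncp = d√(n/2)/√ratio, where n = N/2 per arm; df are N − 2 unadjusted and N − 6 adjusted.
- N = 60: 63% unadjusted; 80 / 74 / 69% adjusted (k = 1); 69 / 64 / 62% (k = 0.7).
- N = 45: 50% unadjusted; 67 / 61 / 55% (k = 1); 55 / 51 / 49% (k = 0.7).

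**Step 4: the mixed model.** The text does not say whether week is categorical, which covariance structure applies, or whether baseline is a response. If baseline is a response with unconstrained arm means, the baseline-to-endpoint contrast behaves like a change score. If arm means are constrained equal at baseline, the precision is already recovered. No single figure follows.

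**Step 5: the strata.** Suppose they explained R² = 5 / 10 / 20% of the variance of change and arms were balanced within strata.
- The unadjusted SE would be too large by the factor 1/√(1 − R²) = 1.026 / 1.054 / 1.118.
- A nominal 5% test would run at 2(1 − Φ(1.96/√(1 − R²))) = 4.4 / 3.9 / 2.8%.

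With allocation not balanced within strata (simulated, N = 60, 6,000 trials per case), the type I error was 5.1 / 5.2 / 5.4%. The simulation error is √(0.05 × 0.95/6000) = 0.3 points, so there is no conservatism.

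**The case against.** These are pilot data, the estimate is valid as planned, and the gain may be small. With k = 0.7 and N = 60, two of the three simulated cases give a gain of at most 3.5% or a slight loss. All of this stands, and it is why the point is a suggestion. It does not remove the case for acting, because the change needs no new data and the worst cost is small.

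The plan also gives a reason for the plain ANOVA: it is meant to inform without the mixed model's missing-data and regression assumptions. That stands too. It argues for placing an ANCOVA beside the ANOVA rather than in its place.

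The plan's reference to covariates already described might point to text outside what was supplied, since part of the document ahead of section E was not available. The absence of pubertal status is therefore a statement about the supplied text only. If the covariates are committed elsewhere, a cross-reference in Prediction 1 settles it.

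A reader might infer more than the documents support:
- **That the result would be biased.** Randomisation protects the estimate.
- **That the main model forgoes 63% against 80% power.** That pair belongs to the change-score analysis at the most favourable assumptions. The mixed model is too loosely specified to quantify.
- **That stratified randomisation without adjustment makes the test conservative.** This requires balance within strata, for example by blocking, and the randomisation text does not state it.

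**Conclusion.** The point holds as a possible improvement in precision and pre-specification. The supplied Prediction 1 text commits to neither baseline score nor any stratum. For the supporting change-score analysis, adjustment would change the variance by between about -35% (the formula value at ρ = 0.3 with equal SDs; -34% after df cost at N = 60) and about +2% at N = 60 or +4% at N = 45. The range rests on the assumed correlations, SD ratios and uninformative strata. For the mixed model the size is unknown, and the part due to baseline could be nil. Any benefit from the strata depends on how prognostic they are and, for test size, on how allocation was balanced. The documents give neither.

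**What to change.** In section E.b, Prediction 1:

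1. **Mixed model.** Model post-baseline CDRS-R and YMRS scores with the baseline score as a covariate and baseline removed from the response. Equivalently, keep baseline as a response with arm means constrained equal at that visit. Do not put baseline on both sides of the model.
2. **Strata.** Include main effects for the ADHD/stimulant stratum (3 levels) and the pubertal stratum. Fix a rule for pooling sparse levels before unblinding.
3. **Supporting analysis.** Add an ANCOVA of endpoint on the same terms. Keep the change-score ANOVA and the raw-change d as the simple check the plan intends. State before unblinding that the adjusted analysis takes precedence.
4. **Prediction 2.** Apply the same to continuous outcomes that have a baseline value. The Teacher's Report Form has one scheduled post-baseline time, so a single ANCOVA suffices there. Keep the adjustment already planned for the mood state of a parent completing the Child Behavior Checklist. The logistic models of functioning need no change, because their response is already defined against the month before baseline.

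The change is to wording only. Baseline is scheduled for everyone on both mood scales, and the strata must be known to randomise. The cost is about 4 degrees of freedom in the ANCOVA, at worst about 2% of variance at N = 60 and 4% at N = 45.

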group2)/pooled standard deviation. We will use a χ^2 test to compare percent responders (defined by CGI-I ≤ 2) at endpoint between treatment groups.

Prediction 2: Omega-3 fatty acid supplementation will be more effective than placebo for improving behavioral symptoms and psychosocial functioning in adolescents with a high risk for developing mania. A MMRM approach will be used to compare change over time in ADHD-RS scores between treatment groups. Additionally, change over time in CBCL and TRF externalizing and internalizing t-scores will be examined using a MMRM model. We will use a χ^2 test to determine whether the percent of subjects > 18 years old (vs. ≤ 18 year old) with completed CBCL and TRF ratings differs significantly between treatment groups. If there is no statistically significant difference, T-scores for 19-21 year olds will be determined using the gender-specific 18 year old t-scores, since we will be examining for group differences in change in score over time. We will use generalized linear mixed logistic regression models to examine change over time in percent responders (defined by achieving a level of functioning that is equal to or better than the month prior to baseline) in each of the four major areas of functioning; role performance, interpersonal relationships, recreational enjoyment, and sexual activity. A mixed effects model repeated measures (MMRM) approach will be used to compare change over time in CGAS scores between treatment groups. We will also evaluate change from baseline to endpoint in CGAS scores and calculate effect sizes as described. Covariates will be included in these models as described above. Additionally, we will examine the effect of change in mood symptom ratings during a specific time period (YMRS and CDRS-R) on change in behavioral and psychosocial functioning during the same time period by using, a repeated-measures framework in SAS PROC MIXED to account for the fact that multiple observations per individual on the same outcome are correlated across time.

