
even the direction) of an association between two variables to depend on the levels of moderating variables. We will assess moderation by the magnitude of the interaction terms in an ANCOVA model where change in mood symptoms is the outcome and the predictors are treatment group, change in metabolite levels, and interactions between metabolite changes and treatment group. A moderated relationship would be consistent with a pattern of results where an association between metabolite levels and mood symptoms exists in the omega-3 fatty acid group, but not in the placebo group. Such an outcome is plausible because placebo response may occur due to mechanisms that are independent of those we hypothesize as causes of treatment response.

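### The repeated-measures models for Predictions 1 and 2 list week and treatment but no treatment-by-week term, so as written they do not estimate the difference in change they are meant to compare

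*Combined protocol and SAP*

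**What the plan says.** Section E.b (Data Analyses), Prediction 1, gives the purpose of the MMRM as to "compare change over time in CDRS-R (and YMRS) scores between treatment (omega-3 vs. placebo) groups". The next sentence gives the terms: "Covariates for these models will be time of assessment (study week) and treatment group". Other covariates are left open ("We will evaluate other potential covariates and confounds as described"); those named are clinical factors (ADHD, anxiety disorders, stimulant use).

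Prediction 2 has repeated-measures models for ADHD-RS, CBCL, TRF and CGAS, and says: "Covariates will be included in these models as described above".

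The Prediction 1 paragraph also has a separate endpoint analysis: "We will also compare treatment group differences in change from baseline to endpoint in YMRS and CDRS-R scores using an analysis of variance (ANOVA"). It adds an effect size d on the same change. CGAS has a similar endpoint evaluation under Prediction 2. None is written for ADHD-RS, CBCL or TRF.

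Interactions are named only under Exploratory analyses. One is in the regressions on baseline measures ("The treatment by change in rating scale interaction term will be the primary measure of interest") and one is in the moderator ANCOVA ("interactions between metabolite changes and treatment group"). Neither is treatment by week.

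On timing, the Assessments section says: "CDRS-R, YMRS, and CGI-S will be administered at screening, baseline (concurrent with the first imaging session) and then subsequently at each weekly follow-up visit". Figure 1 schedules the TRF at baseline and week 12 only. The plan does not say whether the MMRM response is the raw score or change from baseline, and it names no visit contrast.

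**The concern.** In a repeated-measures model of scores, a between-arm difference in change over time is the treatment-by-week interaction. That term is not listed, and no other section supplies it. Two things are at stake.

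The first is the estimand. A group main effect on raw scores answers whether the arms differ in average level over all visits, baseline included. An arm difference already present at baseline and unchanged afterwards would load fully on that term, although neither arm changed more than the other. With 30 per arm, some chance imbalance at baseline is to be expected.

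The second is pre-specification. With neither response nor contrast written down, the treatment test could be taken from the main effect, a slope or the week-12 difference, and the choice could be made after the data are seen.

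**Working it through.** The plan gives no power figure for this model, so there is none to reproduce. The structural point needs no numbers; the size of the loss needs assumptions.

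**Structure.** Let g be 0 for placebo and 1 for omega-3, and t the week.

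- Terms as listed, raw scores: mean = μ_t + βg. The arm difference in change from baseline to week t is [(μ_t + β) − (μ_0 + β)] − [μ_t − μ_0] = 0 for every t. The model has no parameter for it.
- Terms as listed, change from baseline as response: mean = ν_t + γg. γ is one difference in change, common to all visits.
- With treatment-by-week, raw scores: mean = μ_t + δ_t g. The week-12 difference in change is δ_12 − δ_0.

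**Inputs from the documents.** 30 per arm (section E, randomization; section F.2); weekly ratings from baseline to week 12, i.e. 13 time points; d=0.8, the upper end of the range in F.2.

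**Assumptions, not in the documents.** Two-sided alpha 0.05 (none is stated for Prediction 1); complete data; d in units of the single-visit SD; four correlation patterns; two shapes for the effect over time.

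**Formulas.** With equal arms and V the correlation matrix of the visits, generalised least squares gives the group term as Σ w_t δ_t, where w = V⁻¹1/(1′V⁻¹1), with SE = √[(2/n)/(1′V⁻¹1)]. The week-12 contrast has SE = √[(2/n)(2 − 2ρ_0,12)]. Power is from the noncentral t with 58 df.

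**One case in full: linear divergence, constant correlation 0.5, raw scores.** All weights are 1/13.

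- Group term: 0.8 × (78/12)/13 = 0.40, half of 0.8. The variance of a 13-visit mean is (1 + 12×0.5)/13 = 0.538, so SE = √(2/30 × 0.538) = 0.189. The ratio is 2.1 and power is 55%.
- Week-12 contrast: SE = √(2/30 × 1) = 0.258. The ratio is 3.1 and power is 86%.

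**Linear divergence, all cases** (share of the week-12 effect recovered by the group term; power):

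| Correlation | Raw scores | Change from baseline | Week-12 contrast |
|---|---|---|---|
| constant 0.5 | 50%; 55% | 54%; 61% | 86% |
| constant 0.6 | 50%; 48% | 54%; 71% | 93% |
| 0.95^lag | 50%; 41% | 11%; 18% | 89% |
| 0.3 + 0.5×0.85^lag | 50%; 52% | 24%; 20% | 78% |

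**Full effect by week 4, then flat.** Under constant correlation 0.5 the group term recovers 10.5/13 = 81% on raw scores and 10.5/12 = 87.5% on change. Power is 92% and 95%, against 86% for the week-12 contrast, so the group term does better. Under 0.95^lag the same shape gives 52% and 75%, against 89%.

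**TRF, two visits, correlation 0.5, raw scores.** The group term is (0 + 0.8)/2 = 0.40, with SE = √(2/30 × 0.75) = 0.224 and power 42%, against 86% for the difference in change. With change as the response there is only one post-baseline value and no dilution.

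**Scaling check.** With d in units of the SD of the week-12 change, linear divergence, and other correlations (constant 0.5 or 0.7; 0.9^lag or 0.95^lag), the raw-score group term again recovers half. By normal approximation, power is 29-66% against 87% at d=0.8, and 18-43% against 64% at d=0.6.

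**The case against.** The strongest reply is that a list of covariates is not a full model statement. The plan never says main effects only, its stated purpose calls for the interaction, and Prediction 2 again refers to group differences in change. A statistician carrying out that purpose would probably add the term. This is plausible, but it concerns intent. The list is all that is written, and writing the term down costs almost nothing.

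Three stronger readings are tempting, and the documents do not support them.

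- *The model cannot test a difference in change at all.* That holds for raw scores. If the response is change from baseline, the group term tests an averaged difference in change. The plan does not settle which applies.
- *The trial has no sound test of change, or its main efficacy test is the faulty one.* The same paragraph plans an ANOVA and an effect size on endpoint change for CDRS-R and YMRS, and no analysis is named as primary for Prediction 1. The ANOVA does not repair the MMRM, which is the analysis chosen to handle missing data, and it does not extend to ADHD-RS, CBCL or TRF.
- *Much of the power is lost.* That depends on the effect growing slowly or on correlation decaying with time. With an early, sustained effect and constant correlation 0.5, the additive model has more power than the week-12 contrast.

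It is also fair to say that this is pilot work by its own Specific Aims, and that a chance baseline offset does not inflate type I error over repeated randomisations. The estimate would still describe level and not change.

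**Conclusion.** The concern holds as a mismatch between stated purpose and listed terms, in Prediction 1 and by inheritance in Prediction 2. For raw scores the listed model has no parameter for the comparison it is meant to make. For change scores it gives a visit average and not the week-12 effect. This part rests on the text alone.

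The size is conditional. The halving of the effect on raw scores comes from linear divergence and was the same under every correlation tried; the power ranges also depend on the correlation, d and complete data. The documents give neither trajectory nor correlation, so the range runs from a large loss to none. Exposure is greatest for ADHD-RS, CBCL and TRF, which have no written endpoint-change analysis. Should-fix, with high confidence in the missing term and much less in any single power figure.

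**What to change.** In section E.b, state for each repeated-measures model under Predictions 1 and 2:

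- the response (raw score with baseline as one of the visits, or change from baseline);
- the terms treatment, week and treatment-by-week;
- the contrast that tests the prediction, named in advance.

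One suitable choice is categorical week with the week-12 arm difference in change from baseline as the contrast. A treatment-by-linear-time slope would also test change over time, if that is what is wanted; the essential step is to choose before unblinding.

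The cost is a sentence or two of text. With categorical week there are 11 extra parameters for weeks 1-12, or 12 if baseline is a response, which is modest with weekly ratings. If the effect appears early and stays constant, a week-12 contrast can have somewhat less power than an all-visit average (86% against 92-95% in the case above). An average over post-baseline visits could be kept as a named secondary contrast from the same model.
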